6.3 Informed Consent

Prior to enrolling in the study, patients should be fully informed of the details of study participation as required by applicable regulations, the site's IRB/EC, and by sponsor. Informed consent must be obtained from each patient prior to conducting any protocol-induced activities beyond standard of care, by using the informed consent form (ICF) approved by that site's IRB/EC, regulatory authorities as required and by Medtronic, Inc. The ICF must be signed and dated by the patient and by the person obtaining the consent. Any additional persons required by the site's IRB/EC to sign the informed consent form must also comply. In the event the subject cannot read and/or write, a witnessed (impartial third party) ICF will be allowed, provided detailed documentation of the process is recorded in the subject's case history and the witness signs and dates the ICF.

If applicable, independent witness must be present throughout the entire informed consent process, and the written informed consent form and any other information related to the study must be read aloud and explained to the prospective subject. If applicable, witness shall also sign and personally date the consent form to attest that the information in the ICF was accurately explained and clearly understood by the subject, and that informed consent was freely given.

Prior to the patient signing the ICF, the investigator or delegate will fully explain to the patient the nature of the research, study procedures, anticipated benefits, and potential risks of participation in the study. The investigator or delegate will allow adequate time for the patient to read and review the consent form and to ask questions. Signing the ICF serves to document the written and verbal information that the investigator or delegate provides to the patient, the patient's understanding of the information, and his/her agreement to participate. The investigator or delegate must document in the patient's medical records that the patient was consented and the date on which the consent was obtained. The original signed consent form will be retained in the patient's study records and a copy of the informed consent will be provided to the patient. If consent is obtained the same day the subject begins participating in study-related procedures, it must be documented in the subject's case history that consent was obtained prior to participation in any study related procedures. It is best practice for the informed consent process to be documented in the subject's case history, regardless of circumstance.

Patients unable to provide his/her own informed consent, legally incompetent, or otherwise vulnerable are not allowed in the study. Vulnerable subjects include individuals whose willingness to volunteer in a clinical investigation could be unduly influenced by the expectation, whether justified or not, of benefits associated with participation or of retaliatory response from senior members of a hierarchy in case of refusal to participate.

6.4 Revisions in Patient Information and Informed Consent Form

Medtronic will inform the investigators whenever information becomes available that may be relevant to the subject's continued participation in the study. The revised information will be sent to the

investigator for approval by the IRB/EC (as applicable). After approval by the IRB/EC, a copy of this information must be provided to the participating subjects, and the informed consent process as described above needs to be repeated. The investigator or his/her authorized designee should inform the subject in a timely manner.

6.5 Screening and Enrollment

The process of patient screening and subject enrollment is as follows (Figure 2):

1. Patients identified by or presented to the study site with AS will be screened by the investigative team for the subject selection criteria using available medical records, including relevant imaging studies previously performed for diagnostic purposes.
2. If the patient is deemed a potential candidate, all aspects of the study will be explained to the patient. The patient will then be invited to participate in the study. If the patient agrees to participate, written informed consent will be obtained. The date informed consent is signed is considered the point of enrollment, and the subject will be assigned a Subject ID number.
3. The subject will undergo transthoracic echocardiography (TTE) to assess his/her degree of AS and cardiac function.
4. If the site investigative team determines the subject meets AS criteria for severe asymptomatic AS, the qualifying echocardiogram will be submitted to the ECL for confirmation of severity of AS and other echocardiographic criteria.
5. If the ECL confirms echocardiographic criteria are met¹, the subject will undergo the following evaluations:
 - Exercise tolerance testing (ETT), unless contra-indicated
 - Multi-detector computed tomography (MDCT)
 - Pulmonary function testing (simple spirometry with FEV₁)
 - Cardiac MRI
 - Coronary arteriography if there is uncertainty regarding the status of coronary artery disease
6. If the local Heart Team considers the subject suitable for implantation, the following information should be submitted to the ERC:
 - Clinical assessments including medical history, co-morbidities, and symptomology
 - TTE data on degree of AS and cardiac function
 - MDCT data on anatomical suitability
7. The ERC will review the submitted information and either confirm, disapprove, or defer eligibility for implantation. Subjects confirmed eligible for implantation should undergo TAVR within 90 days of ERC approval. Subjects disapproved should be exited from the study, and not be reconsidered for future participation without permission from Medtronic.

¹If a subject has balloon aortic valvuloplasty after their qualifying TTE, they must have repeat TTE to confirm he/she meets criteria for aortic stenosis prior to submission to the ERC.

[figure not shown]

Figure 2. Flow diagram of the study entry process. Patients should give written consent before undergoing any protocol-required testing. However, if any of protocol-required baseline/screening evaluations (e.g. echocardiography, ETT, MDCT, lab work) have been performed for diagnostic purposes or standard of care prior to consenting, they can be used as the protocol-required exams, provided they are within the protocol-required time windows and contain the necessary information.

6.6 Required Evaluations

Protocol required evaluations should be performed at the study site. The protocol required evaluations are as follows and summarized in Table 1. Additional information on data collection requirements is provided in Section 6.13 through Section 6.18. As this is an interventional study, some or all of the required study procedures may be outside of standard of care for a given patient.

Baseline (within 12 weeks prior to submission to the Eligibility Review Committee²)

- Clinical assessment and medical history, including NYHA classification
- Coronary arteriography (may be either selective or by computed tomography)
- Transthoracic echo (TTE)
- Exercise Tolerance Test (ETT)³
- Cardiac MRI
- Simple spirometry (timed vital capacity with FEV₁)
- MDCT (peripheral vasculature and aortic annulus)
- 12-lead ECG
- Complete blood count
- pro B-type natriuretic peptide (NT-proBNP)
- Heart Team assessment
- Six-minute walk test (6MWT)
- Modified Rankin Score
- Quality of Life Questionnaires:
 - Kansas City Cardiomyopathy Questionnaire (KCCQ)
 - European Quality of Life – 5 Dimensions (EQ-5D)
- Medications
- Adverse events

Implant Procedure

- Pre-deployment hemodynamics (LV and aortic pressures)
- Aortography (final result)
- Adverse events and device deficiencies

Discharge

- Clinical assessment (NYHA not assessed at discharge)
- 12 lead ECG
- Medications
- TTE⁴
- Adverse events and device deficiencies

30 days (between 30 to 45 days post implant)

² Pre-implant MDCT and coronary arteriography should be performed within 365 days of submission to the eligibility review committee

³ Unless subject has contra-indication for ETT

⁴ Discharge TTE should be performed ≥ 12 hours and ≤ 7 days post procedure

- Clinical assessment, including NYHA classification
- 12 lead ECG
- TTE
- Medications
- Adverse events and device deficiencies
- KCCQ

6 Months (between 183 to 210 days post implant)

- Clinical assessment, including NYHA classification
- 12 lead ECG
- TTE
- Medications
- pro B-type natriuretic peptide (NT-proBNP)
- Quality of Life Questionnaires:
 - Kansas City Cardiomyopathy Questionnaire (KCCQ)
 - European Quality of Life – 5 Dimensions (EQ-5D)
- Cardiac MRI
- Six-minute walk test (6MWT)
- Adverse events and device deficiencies

1 Year (between 365 to 395 days post implant)

- Clinical assessment, including NYHA classification
- TTE
- Medications
- KCCQ
- Adverse events and device deficiencies

2 Years (between 730 to 760 days post implant)

- Clinical assessment, including NYHA classification
- TTE
- Medications
- KCCQ
- Adverse events and device deficiencies

3 Years (between 1095 to 1125 days post implant)

- Clinical assessment, including NYHA classification
- TTE
- Medications
- KCCQ
- Adverse events and device deficiencies

4 Years (between 1460 to 1490 days post implant)

- Clinical assessment, including NYHA classification
- TTE
- Medications

- KCCQ
- Adverse events and device deficiencies

5 Years (between 1825 to 1855 days post implant)

- Clinical assessment, including NYHA classification
- TTE
- Medications
- KCCQ
- Adverse events and device deficiencies

Other Evaluations

- Suspected stroke events should be confirmed by neurology consult and neuroimaging per site’s standard practice. A Modified Rankin Score assessment should be conducted at 1 and 3 months following any confirmed stroke event.
- The investigative team should follow their standard practices for assessment of suspected myocardial infarction, acute kidney injury, neurological events, prosthetic valve endocarditis, prosthetic valve thrombosis, etc.
- Non-protocol echocardiograms (e.g. performed for suspicion of prosthetic valve dysfunction) should be submitted to the ECL for evaluation.

Table 1. Summary of required evaluations and visit schedule

	Baseline	Implant	Discharge	30 Days	6 Months	Annual through 5 Years	1 month post stroke event	3 months post stroke event
Clinical assessment including NYHA	✓ ⁵		✓ ¹	✓	✓	✓		
Transthoracic Echo	✓		✓ ⁴	✓	✓	✓		
Multi-detector CT	✓							
12-lead ECG	✓		✓	✓	✓			
Coronary arteriography	✓							
Exercise Tolerance Test (unless contraindicated)	✓							
Cardiac MRI	✓				✓			
6-Minute Walk Test	✓				✓			
Spirometry	✓							
Complete Blood Count	✓							
Pro B-type natriuretic peptide	✓				✓			

Heart Team Assessment	✓							
Aortography		✓						
Hemodynamics		✓						
Medications	✓		✓	✓	✓	✓		
KCCQ	✓			✓	✓	✓		
EQ-5D	✓				✓			
Modified Rankin Score	✓						✓	✓
Adverse Events and/or device deficiencies ²	✓	✓	✓	✓	✓	✓		

Notes

1. NYHA not required at discharge
2. Adverse events should be assessed and captured at each follow-up visit after time of informed consent.
3. Discharge TTE used for “Device Success” should be performed > 12 hours and ≤ 7 days post implant
4. Clinical assessment and medical history required at baseline

Visit Windows

Baseline	Within 12 weeks prior to submission to ERC (except for MDCT and coronary arteriography)
Discharge	At the time of discharge from index TAVR procedure (at least 12 hours post-procedure) or within 7 days post implant, whichever comes first
30 Days	Between 30 and 45 days post implant
6 Months	Between 183 and 210 days post implant
1 Year	Between 365 and 395 days post implant
2 Years	Between 730 and 760 days post-implant
3 Years	Between 1095 to 1125 post-implant
4 Years	Between 1460 to 1490 days post-implant
5 Years	Between 1825 to 1855 days post-implant

6.7 Subject Disposition

Sites will maintain a log of subjects consented, the subject ID numbers assigned to them, and the dates of their implants (or attempted implants). Subjects who are consented but are not taken to the procedure room for implantation should be exited from the study and need not be followed beyond the date of study exit.

Subjects taken to the procedure room for implantation, and any of the following occurred: anesthesia administered, vascular line placed, TEE placed or any monitoring line placed, but do not receive a TAV for any reason should be followed for safety events for 30 days after the procedure or through the hospitalization, whichever is longer, and then exited from the study. Subjects that have their TAV explanted should be followed for safety events for 30 days after the explant procedure, or through resolution of related adverse events, whichever is longer, then exited from the study.

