5.1 Number of Subjects, Duration, and Number of Investigational Devices

This study will involve up to 75 subjects implanted with the study device among all active sites. As not all patients consented for evaluation will go forward to implantation, the number of subjects consented for the study is expected to be higher (up to 150). No site will implant more than 15 subjects without prior authorization from Medtronic in order to minimize bias.

Subjects will be consented for follow-up through five years following implantation, and all implanted subjects will be followed per protocol through five years following implantation. Subjects who exit from the study after implantation will not be replaced. The enrollment period is estimated to be between 9 and 20 months, and the estimated total study duration (first subject implanted to last subject completing his/her last follow-up exam) is estimated to be seven years.

The number of investigational TAVR systems involved in this study is estimated to be between 75 and 150 (inclusive of devices used during index implantation procedures, devices opened but not used, and devices shipped to sites as inventory for the study but not opened or used).

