6.11 Subject Withdrawal or Discontinuation

All subjects will be encouraged to remain in the study through the last follow-up visit at five years. Subjects who discontinue participation prematurely will be included in the analysis of results (as appropriate) and will not be replaced in the enrollment of total study subjects. If a subject is discontinued from the study early, the reason for discontinuation should be documented in the subject file and a Study Exit eCRF must be completed.

The study site should make every effort to have all subjects complete the follow up visit schedule. When subjects are lost to follow-up the investigator will make efforts to confirm the vital status of the subject, as described in the informed consent. A subject will not be considered lost to follow-up unless all efforts to obtain compliance are unsuccessful. At a minimum, the efforts to obtain follow-up information must include 3 attempts to make contact via telephone and if contact via phone is not successful, a traceable letter from the investigator should be sent to the subject's last known address. The study site may also utilize a civil register for subject information, as applicable. Should both telephone and mail efforts to contact the subject be unsuccessful, the subject's primary physician should be contacted. Subjects will then be deemed lost to follow up. All contact efforts to obtain follow-up must be documented in both the subject's medical records and on the study eCRFs.

If a subject discontinues the study at any time, is withdrawn from the study early, or completes all protocol required follow-up they should continue to be followed by the implanting site according to their routine clinical practice for patients with prosthetic aortic valves. If for any reason this is not possible for a particular subject, or if a subject needs to change their follow-up site at any time point after conclusion of the study, investigators should refer subjects to a local site with appropriate training and experience in managing patients with prosthetic aortic valves. Study data will not be collected after a subject has ended their participation in the study.

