7.4 Handling of Missing, Unused, and Spurious Data and Dropouts

Every effort will be undertaken to minimize missing data. Missing (accidentally, due to withdrawal, missing follow-up or loss to follow-up, etc.), unused and spurious data will remain identifiable in the database. For time-to-event outcomes, dropouts will be censored at the time of discontinuation, consistent with the Kaplan-Meier approach. Unless otherwise specified, all analyses will be based on available data and missing data will not be imputed. The number of subjects included in each analysis will be reported so that the reader can assess the potential impact of missing data.

In the case of partial dates, unknown portions will be imputed for the purposes of analysis. If only the month and year are known, the event or assessment will be analyzed as if it occurred on the 15th of the known month. If only the year is known, the event or assessment will be analyzed as if it occurred on June 30th of the known year. Imputation of partial dates is subject to the restriction that pre-implant events must occur between the date of informed consent and the date of implant and post-implant events must occur after the date of implant.

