7.9 Evaluation of Objectives

7.9.1 Safety Endpoints

The following safety endpoints are defined and will be analyzed:

1. All-cause and cardiovascular mortality at 30 days and 6 months
2. All stroke (disabling and non-disabling) at 30 days and 6 months
3. Myocardial infarction (periprocedural and spontaneous) at 30 days and 6 months
4. Acute kidney injury at 30 days and 6 months
5. Major vascular complications at 30 days and 6 months
6. Life-threatening bleed at 30 days and 6 months
7. New permanent pacemaker implantation (PPI) at 30 days and 6 months
8. New intraventricular conduction delays at 30 days and 6 months
9. New-onset atrial fibrillation at 30 days and 6 months
10. Valve-related dysfunction requiring repeat procedure at 30 days and 6 months

Safety endpoints will be adjudicated by the Clinical Events Committee (CEC) and analysis will be based on data collected on the CEC adjudication form. Safety endpoints will be analyzed with Kaplan-Meier survival analysis methods according to Section 7.2. Safety endpoints will be analyzed using the Attempted Implant population.

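### Subjects who exit after a failed attempt or an explant are censored, so Attempted Implant event rates at 6 months and later may be understated by an unknown amount

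*Protocol*

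**What the plan says.** Protocol 6.7 has two exit rules for subjects who reached the procedure room:

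- **Attempted, no valve received, whatever the reason:** safety follow-up for "30 days after the procedure or through the hospitalization, whichever is longer, and then exited from the study".
- **Valve explanted:** "Subjects that have their TAV explanted should be followed for safety events for 30 days after the explant procedure". The rest of that sentence extends follow-up until any related events have resolved, if that is later, and then requires study exit.

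Thirty days is therefore a minimum in both cases, but exit is mandatory. Protocol 6.11 adds: "Study data will not be collected after a subject has ended their participation in the study". The vital-status tracing in 6.11 is written for subjects lost to follow-up, not for those whom the protocol itself exits.

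SAP 7.4 states: "For time-to-event outcomes, dropouts will be censored at the time of discontinuation, consistent with the Kaplan-Meier approach". SAP 7.2 sets the censoring date of an event-free subject at the last visit, assessment or event. SAP 7.9.1 states: "Safety endpoints will be analyzed using the Attempted Implant population". SAP 7.9.2.2 and 7.9.2.3 use the same set and method for hospitalizations and heart failure events, and SAP 7.9.3 carries the matching outcomes annually to five years. Missing data are not imputed, and no sensitivity analysis for exits is planned.

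Protocol 5.1 states: "Subjects will be consented for follow-up through five years following implantation". It and SAP 5.3 also say that all implanted subjects are followed through five years. The explant exit in 6.7 is not mentioned there.

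**The concern.** The Attempted Implant set exists so that outcomes are counted in everyone in whom the procedure was started. After about day 30 the protocol stops observing some of its members, and what selects them is that the valve was not placed or was later removed. Kaplan-Meier treats a censored subject as having the same later risk as those still under observation. Here that equality has no design support and cannot be checked, because nothing is recorded after exit.

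The rates matter beyond this study. Protocol 4.1 makes event-rate estimation for pivotal studies a primary objective, and Protocol 5.2 says that the rates feed pivotal sample-size estimates. With about 75 subjects, one or two unseen events would shift a rate noticeably.

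**Working it through.** **Who can be lost, and when.** SAP 7.2 places 6 months at day 183 and 5 years at day 1825.

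- A non-implanted subject can be censored from about day 30.
- A subject explanted on day d can be censored from day d + 30. That falls before day 183 if d < 183 − 30 = 153, and before day 1825 if d < 1825 − 30 = 1795. Adverse events that resolve later push the exit back.
- Since d + 30 is never below 30, the 30-day rates are largely protected for both groups.

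**Is there a figure to reproduce?** No. The documents give no expected event rate, explant rate or non-implant rate. Except for the time points above, every input below is an assumption. N = 75 borrows the planned implant number; the Attempted Implant set could be slightly larger.

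**Six months.** Let k of N subjects exit event-free at day 30. Let p0 be the risk to day 30, p the risk from day 30 to 183 in retained subjects, and q the same risk in exited subjects.

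- Expected Kaplan-Meier rate: 1 − (1 − p0)(1 − p)
- Rate under full follow-up: 1 − (1 − p0) × [(N − k)(1 − p) + k(1 − q)] / N
- Difference: (1 − p0) × (k/N) × (q − p)

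With p0 = p = 1% and k = 3, Kaplan-Meier gives 1 − 0.99 × 0.99 = 1.99%.

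| q (exited) | Full follow-up | Understatement, points |
|---|---|---|
| 1% (equal risk) | 1.99% | 0.00 |
| 10% | 2.35% | 0.36 |
| 25% | 2.94% | 0.95 |
| 50% | 3.93% | 1.94 |

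For example, at q = 10%: 0.99 × 3/75 × 0.09 = 0.36 points. Over k = 1 to 6 and q = 10% to 50%, the range runs from 0.99 × 1/75 × 0.09 = 0.12 to 0.99 × 6/75 × 0.49 = 3.88 points.

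**Five years.** Assume 3% annual risk in retained subjects and, for simplicity, exits at the outset. Kaplan-Meier gives 1 − 0.97⁵ = 14.13%. With k = 3, full follow-up is 1 − [72 × 0.97⁵ + 3 × (1 − q)⁵] / 75, where q is now the annual risk in exited subjects: 14.63%, 15.20% and 16.25% for q = 6%, 10% and 20%.

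**Bounds that need no assumption about the exited subjects' risk.** With 2 events after day 30 and 3 subjects censored at day 30, Kaplan-Meier gives 2/72 = 2.78%. The rate in all 75 lies between 2/75 = 2.67% (no exit has an event) and 5/75 = 6.67% (all do).

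**The case against.** **The effect may be small or absent.** No document says that exited subjects are at high risk. A subject counts as attempted once a monitoring line is placed, so a non-implant need not mean a device failure. The population is asymptomatic with preserved ejection fraction. This stands: with equal later risk the bias is zero, and with lower risk Kaplan-Meier would overstate the rate.

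**Much is still counted.** Events before exit are kept. A repeat procedure for valve dysfunction, including surgical replacement, is itself a safety endpoint (Protocol 13.8.1). Acute kidney injury is limited to 7 days and periprocedural infarction to 72 hours. Unresolved related events or long admissions extend follow-up. This also stands, and it narrows the exposure mainly to later death, stroke, hospitalization and heart failure events.

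**The SAP already shows some of it.** SAP 7.1.1 tabulates attempted and implanted subjects, SAP 7.2 reports numbers at risk, and SAP 7.4 reports the number in each analysis. Non-implants can be found by subtraction. Exits after explant have no category of their own.

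**The estimates are imprecise anyway.** The study is descriptive. Exact 95% intervals are 0.03% to 7.2% for 1/75 and 0.3% to 9.3% for 2/75, so one missed death lies well within sampling error. That is true, but an interval does not allow for systematic loss, and pivotal planning will use the point estimates.

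**Stronger readings that a reader might infer.** One is that the reported 6-month death rate could be half the true one: one observed death (1/75 = 1.3%) plus one unseen death among three exits (2/75 = 2.7%). That implies about 33% mortality in the exited group over roughly five months, for which the documents offer nothing. Another is that quality of life is biased in the same way, but the Kaplan-Meier argument does not apply to KCCQ change scores.

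**Conclusion.** The point holds as a possible bias of unknown size. Exit is mandatory, data stop at exit, exits are censored, and Attempted Implant remains the analysis set for safety, hospitalization and heart failure events at 6 months and annually. Because exit is linked to procedural or device outcome, non-informative censoring cannot be assumed, and later death, stroke, hospitalization and heart failure rates may be understated.

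The documents do not show that the assumption is false, that the exited subjects are those at highest risk, or that the rates are in fact biased in the device's favour. Under the stated assumptions with 3 exits of 75, the 6-month shift runs from nothing to about 1.9 points. It rests wholly on the assumed number of exits and their assumed later risk. This is a cheap improvement worth making, not a flaw that undermines the study.

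**What to change.** - **Protocol 6.7:** for all Attempted Implant subjects who consent, continue to collect vital status and key safety events by telephone or record check at 6 months and annually. The contact route in 6.8 is written for missed visits and would need extending. Check the consent wording for non-implanted subjects, since 5.1 frames consent as follow-up after implantation.
- **Protocol 6.7 against Protocol 5.1 and SAP 5.3:** reconcile the explant exit with the statement that all implanted subjects are followed through five years.
- **SAP 7.1.1 and 7.4:** report the number censored because of non-implant exit and, separately, explant exit. Add best-case and worst-case bounds for all-cause mortality and stroke at 6 months and annually. Do not score each exit as a failure on every key safety endpoint: that would record a death, a stroke, a new pacemaker and valve dysfunction in someone who may never have received a valve, with no matching best case.

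The cost is a few contacts for what are likely to be very few subjects, a protocol amendment and possibly new consent wording. The SAP part is wording and a short table, and can be done even if follow-up is not extended.
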